7.2 Study Design

Fourteen relapsed/ refractory AML patients with FLT3 activating mutations will be treated with crenolanib daily as reinduction until they meet one of the criteria for discontinuation. After HSCT, patients who received crenolanib prior to transplant and achieved response may continue on study post-transplant with maintenance crenolanib. Until they meet one of the criteria for discontinuation. Subject efficacy evaluations will be performed at scheduled time points. These include: monthly bone marrow biopsy in the first two months, and then every three months for as long as criteria for CR/CRi is maintained. At loss of CR/CRi, bone-marrow biopsy will be performed only as clinically indicated to exclude toxicity issues such as pancytopenia due to study drug versus myelosuppression from progressive AML. Subjects' best clinical response will be recorded, as well as the response at 2 months. Subjects not in CR/Cri by the end of month 2 but showing clinical benefit will be allowed to continue therapy at the discretion of the physician.

7.3 Supportive Care Guidelines

Supportive measures including blood and platelet transfusions, antimicrobials, etc. are permitted. The administration of hematopoietic colony stimulating factors is not permitted.

Other chemotherapy, investigational cytotoxic agents, radiation, or biologic therapy is prohibited while the subject is on study with the following exceptions during cycle 1:

- 1. During the first 5 days of cycle 1 of study only, subjects may receive leukapheresis (not more than three procedures per week and not more than five procedures in total) to control elevated blast and/or platelet counts
- 2. hydroxyurea (up to a maximum of 5 gm /day) for a maximum of 14 days may be administered during cycle 1.
- 3. Leukapheresis and hydroxyurea may be administered together according to the guidelines above.

8. Study Procedures

After providing informed consent, if meeting the screening inclusion/exclusion criteria, and after having baseline evaluations performed within 28 days prior to first dose of study drug patients will be enrolled in the study.

The following assessments will be performed after completion of the informed consent and within 28 days of start of study drug except as otherwise specified:

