- 1. For patients with active relapse and given as reinduction, 200mg/m²/day divided in three doses daily (preferably every eight hours), taken orally at least 30 minutes pre or post meal. Patients will complete a daily diary to record the date, time and amount (number of tablets) of crenolanib taken and eating schedule. (Appendix III) Concurrent hydroxyurea (maximum 5g total daily dose) is permitted for the first 14 days of study therapy.
- 2. For patients continuing therapy as maintenance after allogeneic stem cell transplant (HSCT), the same dose of crenolanib most recently tolerated by the patient during induction will be restarted. Patients will complete a daily diary to record the date, time and amount (number of tablets) of crenolanib taken and eating schedule (Appendix III)

Planned Duration of Treatment:

The anticipated duration of patient involvement is a minimum of 28 days with a maximum of 365 days but assessed individually for each patient. Subjects will take crenolanib besylate daily as reinduction and may resume as maintenance after allogeneic stem cell transplant, until their disease has progressed, the patient has died, or the patient discontinues for adverse events, investigator's judgment, or other reasons.

Subjects who have discontinued will continue to be followed 30-days post last dose.

Reference Therapy, Dose and Mode of Administration:

No comparators will be used.

Criteria for Evaluation:

International Working Group for AML (Cheson, et. al., JCO, 2003)

Statistical Methods:

Protocol: ARO-004

The primary end-point is overall response rate. Descriptive statistics will be presented for all categories of each best response category. Duration of response and PFS will be listed and additionally summarized using Kaplan-Meier methodology. In addition, if at any time unacceptable toxicity is encountered in more than 33% of patients, the accrual will stop and lower doses may be investigated.

4. Abbreviations and Definitions

Adverse Event (AE)

Any untoward medical occurrence in a patient or clinical investigation subject administered a pharmaceutical product and which does not necessarily have a causal relationship with this treatment. An adverse event can therefore be any unfavorable and unintended sign (including an abnormal laboratory finding), symptom, or disease temporally associated with the use of a medicinal (investigational) product, whether or not related to the medicinal (investigational) product.

Audit

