8.2 Evaluation during Treatment and Post Allogeneic Transplant

- 1. Patient visits are weekly (± 2 days) for Cycle-1, bi-weekly (± 4 days) for Cycle-2, once every cycle (±14 days) from Cycle-3 to Cycle-6, once every two cycles (± 1 cycle) thereafter. The flexibility is applied to all instances unless specified.
- 2. Physical exam at the start of each cycle (\pm 4 days) for the first 2 cycles, then every 2 cycles and documentation of all concomitant medications.
- 3. EKG measurements to be obtained at 1 hour (± 30 mins) post first or second dose, in accordance to the visit. If new drugs with known effect on QTc are to be coadministered with crenolanib, EKGs including a baseline prior to start of the new agent and 2-3 days after starting patient on combination of drugs is recommended. Weekly EKG x3 is also recommended for follow up and as needed for assessment based on patient's clinical condition. EKG can then be resumed per study schedule.
- 4. CBC with platelet count, differential (differential may be omitted if WBC is $<0.5 \times 10^9$ /L) twice weekly (at least 24 hours apart) for the first two weeks of cycle 1, once weekly (\pm 3 days) for the second two weeks of cycle 1, bi-weekly (\pm 4 days) for the second cycle and once a month thereof from cycle 3 until cycle 12 (\pm 14 days).
- 5. Creatinine, total bilirubin, ALT, AST, twice weekly (at least 24 hours apart) for the first two weeks of cycle 1, once weekly (±3 days) for the second two weeks of cycle 1, biweekly (±4 days) for the second cycle and once a month thereof from cycle 3 until cycle 12 (± 14 days).

- 6. Bone marrow aspiration (with two additional aspirates) should be taken at these time points: cycle 2 day 1 (+4 days), then cycle 3 day 1 (+/- 4 days). Following which every 3 cycles (+/- 1 cycle) as long as criteria for CR are maintained. At loss of CR, bone-marrow biopsy would be performed only as clinically indicated to exclude toxicity issues like persistent pancytopenia due to study drug vs. from progressive AML. Aspiration sample for study purposes may also be submitted for patients not in CR if a marrow will be done for clinical purposes. Handling of bone marrow specimens is outlined in section 8.13, lab manual, and appendix XI.

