8.9 Concomitant Therapy

All supportive therapy for optimal medical care will be given during the study period at the discretion of the attending physician(s) within the parameters of the protocol and documented on source documents as concomitant medication.

No other anticancer therapy including immunotherapy, hormonal cancer therapy, or experimental medications other than hydroxyurea (which is allowed during the first two weeks) will be permitted while patients are participating in this study. Radiation therapy will not be allowed. No hematopoietic growth factors will be permitted while patients are participating in this study. Any disease progression requiring other forms of specific antitumor therapy will be cause for discontinuation of study therapy.

At the discretion of the investigator, crenolanib can be administered with standard anti-emetic and anti-diarrheal premedication. Prophylaxis can be discontinued if patient tolerates crenolanib without significant nausea and vomiting.

Donor lymphocyte infusion (DLI) will be permitted after 2 cycles (56 days) of crenolanib therapy exclusive of any drug hold for resolution of toxicity.

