8.12 Follow up Visits

The Study Schedule in Appendix IV lists the specific follow up visits for this study.

The Study Schedule applies to patients receiving study drug. The calendar should re-commence as start of cycle 1 when drug is resumed post allogeneic transplant. Patients who have discontinued study drug for any reason should be followed for survival.

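### Section 7.3 allows hydroxyurea on any 14 days of cycle 1, while the synopsis and 8.9 allow it only in the first 14 days, so the gap before the first response marrow is 1–5 or 15–19 days

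*Combined protocol and SAP*

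**What the plan says.** Three places set the hydroxyurea window.

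- **Section 7.3, item 2** caps the daily dose at 5 g and lets the drug be given "for a maximum of 14 days may be administered during cycle 1". It sets a duration but no start or end day. The item just before it, on leukapheresis, does fix calendar days: "During the first 5 days of cycle 1 of study only, subjects may receive leukapheresis".
- **Synopsis**, under test product and dosage: "Concurrent hydroxyurea (maximum 5g total daily dose) is permitted for the first 14 days of study therapy".
- **Section 8.9** bars other anticancer treatment on study, "other than hydroxyurea (which is allowed during the first two weeks) will be permitted".

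The exclusion criteria in 6.2 also exempt hydroxyurea, but give no window. No section says which text takes precedence.

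Section 8.2, item 6, schedules on-treatment marrows at "cycle 2 day 1 (+4 days), then cycle 3 day 1", the second with 4 days either side. Section 7.2 records both best response and the response at 2 months. Section 9.1 requires, for CR and CRi, blood free of blasts together with marrow criteria. It asks for no confirmatory assessment and no hydroxyurea-free interval. Section 10.3.4 makes any analysis relating concomitant medication to outcome optional.

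**The concern.** Overall response rate is the primary endpoint of a 14-patient trial with no comparator, and it is read as crenolanib's own activity. Section 7.3 introduces hydroxyurea as an exception to its ban on other chemotherapy. If hydroxyurea can be given up to the day before the first response assessment, the blood counts and circulating blasts seen then may partly reflect it. Because best response is recorded without confirmation, a single cycle 2 day 1 reading can become a patient's result. Sites following different sections would also give hydroxyurea on different schedules, and the planned analysis would not necessarily show it.

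**Working it through.** The plan states no figure on this point, so there is nothing to reproduce. The check is day arithmetic on the protocol calendar.

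Inputs:
- A cycle is 28 days (8.3), so cycle 2 day 1 is 28 + 1 = day 29 and cycle 3 day 1 is 56 + 1 = day 57.
- Held or missed doses do not shift the count (8.3). I assume no cycle delay under 8.7.4.
- First marrow, window +4 days (8.2): day 29 to 33.
- Second marrow, window ±4 days (8.2): day 57 − 4 = 53 to 57 + 4 = 61.
- Last permitted hydroxyurea day: 14 under the synopsis and 8.9; 28 under 7.3 read alone, if the 14 days used are days 15–28.

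Formula: gap = marrow day − last permitted hydroxyurea day.

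| Text applied | Last day | Gap to first marrow | Gap to second marrow |
|---|---|---|---|
| Synopsis and 8.9 | 14 | 29 − 14 = 15 to 33 − 14 = 19 days | 53 − 14 = 39 to 61 − 14 = 47 days |
| 7.3 alone | 28 | 29 − 28 = 1 to 33 − 28 = 5 days | 53 − 28 = 25 to 61 − 28 = 33 days |

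The two readings differ by 28 − 14 = 14 days at each assessment. By the second marrow the gap is at least 25 days on either reading, so the issue is mainly one for the first assessment.

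Which parts of the response could be touched? In 9.1, CR and CRi need no circulating blasts, and neutrophil and platelet counts decide between them. Those are blood elements. Both categories also need low marrow blasts, no Auer rods and no extramedullary leukemia. The documents give no data on what hydroxyurea does to any of these, so no bias in the response rate can be calculated. If one assumes that it lowers blood counts generally, the direction is mixed. Clearance of circulating blasts would be helped and count recovery hindered. A patient moved from CR to CRi by low counts still counts as a responder, while low counts could hide a partial remission or hematologic improvement.

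**The case against.** The best defence is that the three texts can all be met at once: hydroxyurea on days 1–14 satisfies every one of them. Section 8.9 is worded as a prohibition, so use on day 20 would breach it whatever 7.3 says. The short gap arises only at a site that follows 7.3 and overlooks the other two passages. This stands, and it rules out reading the protocol as a whole as permitting days 15–28. It does not remove the inconsistency, because nothing ranks the sections and 7.3 is where a site would look for supportive-care rules.

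Existing safeguards also count. The 2-month response is recorded, duration of response is summarised by Kaplan-Meier (10.3.7), and concomitant medications are documented. A fleeting response would therefore leave a trace. None of these, however, ties hydroxyurea dates to the response assessment as a planned output.

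A reader might go further and infer three things that the documents do not support:

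- **That a whole CRi, 1/14 = 7.1 percentage points, could be credited to hydroxyurea.** The marrow criteria must be met too, and nothing shows that hydroxyurea meets them. Section 8.6 does report unsustained blast reductions at the earlier dose, but lists those 6 patients apart from the 4 with CR or CRi. It is not evidence that transient reductions were scored as response.
- **That the exception reopens after transplant and affects the endpoint.** Section 8.12 says: "The calendar should re-commence as start of cycle 1 when drug is resumed post allogeneic transplant". That concerns the study calendar. Section 9.1 limits responders to patients treated as reinduction, so the primary endpoint is not reached.
- **That early responses must be confirmed at cycle 3 day 1 to count.** This is a debatable trade-off. A responder who goes to transplant before that visit could not be confirmed and might be dropped, although bridging to transplant is a study objective.

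**Conclusion.** The inconsistency is real and should be removed. Read alone, 7.3 allows a gap of 1–5 days between the last hydroxyurea dose and the first response marrow; the synopsis and 8.9 imply 15–19 days. The supported consequence is limited: the blood component of the cycle 2 day 1 reading could be affected at a site relying on 7.3. Neither the size nor the direction of an effect on the response rate can be derived, and the number of patients who would receive hydroxyurea late in cycle 1 is not given. The day counts assume an undelayed 28-day first cycle and use of the latest days that 7.3 allows.

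**What to change.** 1. The sponsor must reconcile the synopsis, 7.3 and 8.9 so that all three state the same hydroxyurea window. Which window is a clinical decision, and none is proposed here.
2. Add a listing to 10.3.7: for each responder, the first and last hydroxyurea dates from the concomitant medication records, beside the date of the blood and marrow assessment that established the response. Check that the CRF captures both dates.
3. Report the 2-month response, already recorded under 7.2, alongside best response. Show patients with no assessment at that time, for example because of transplant, as not assessed.

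The cost is wording in three places, one listing and one extra summary. No visit, sample or marrow is added, and no responder is removed from the primary analysis.

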8.1 Baseline Screening

- 1. Medical history (includes documentation of current medications and allergies)
- 2. Height, weight, vital signs ECOG Performance Status (Appendix II)
- 3. Pregnancy test for women of child bearing capacity
- 4. A complete history and physical, documentation of all disease, concomitant medications and performance status
- 5. CBC, platelet count, differential
- 6. Creatinine, total bilirubin, ALT, and AST
- 7. Bone marrow aspirate within 14 days preceding study drug initiation. Cytogenetics will be obtained prior to therapy (results from prior analysis can be used for this purpose, if done within 6-months of enrollment)
- 8. Evaluation of FLT3-D835, FLT3-ITD and other mutational status (if not done < 60 days preceding study drug initiation).
- 9. Baseline EKG assessment

8.2 Evaluation during Treatment and Post Allogeneic Transplant

- 1. Patient visits are weekly (± 2 days) for Cycle-1, bi-weekly (± 4 days) for Cycle-2, once every cycle (±14 days) from Cycle-3 to Cycle-6, once every two cycles (± 1 cycle) thereafter. The flexibility is applied to all instances unless specified.
- 2. Physical exam at the start of each cycle (\pm 4 days) for the first 2 cycles, then every 2 cycles and documentation of all concomitant medications.
- 3. EKG measurements to be obtained at 1 hour (± 30 mins) post first or second dose, in accordance to the visit. If new drugs with known effect on QTc are to be coadministered with crenolanib, EKGs including a baseline prior to start of the new agent and 2-3 days after starting patient on combination of drugs is recommended. Weekly EKG x3 is also recommended for follow up and as needed for assessment based on patient's clinical condition. EKG can then be resumed per study schedule.
- 4. CBC with platelet count, differential (differential may be omitted if WBC is $<0.5 \times 10^9$ /L) twice weekly (at least 24 hours apart) for the first two weeks of cycle 1, once weekly (\pm 3 days) for the second two weeks of cycle 1, bi-weekly (\pm 4 days) for the second cycle and once a month thereof from cycle 3 until cycle 12 (\pm 14 days).
- 5. Creatinine, total bilirubin, ALT, AST, twice weekly (at least 24 hours apart) for the first two weeks of cycle 1, once weekly (±3 days) for the second two weeks of cycle 1, biweekly (±4 days) for the second cycle and once a month thereof from cycle 3 until cycle 12 (± 14 days).

- 6. Bone marrow aspiration (with two additional aspirates) should be taken at these time points: cycle 2 day 1 (+4 days), then cycle 3 day 1 (+/- 4 days). Following which every 3 cycles (+/- 1 cycle) as long as criteria for CR are maintained. At loss of CR, bone-marrow biopsy would be performed only as clinically indicated to exclude toxicity issues like persistent pancytopenia due to study drug vs. from progressive AML. Aspiration sample for study purposes may also be submitted for patients not in CR if a marrow will be done for clinical purposes. Handling of bone marrow specimens is outlined in section 8.13, lab manual, and appendix XI.
- 7. Samples for translational research including pharmacokinetic analysis, whole-blood phospho-flow cytometry and plasma inhibitory assay will be obtained as defined in section 8.13.and lab manual. For patients that remain on study with no significant toxicity for more than 12 months, subsequent evaluations during study may be modified after discussion with the sponsor. These may include a decrease in frequency of bone marrow aspirations to every 6-12 months (or as clinically indicated), correlative studies to every 6-12 months (or suspension of sample collection for correlative studies), and other laboratory tests to once every cycle.
- 8. Procedures that are to be performed at the planned patient visits will be granted an exception only if the patients are hospitalized and unable to travel to the study sites. In that case, the investigator is responsible to ensure that the planned protocol procedures are performed at a local hospital. Source documents shall be obtained and information recorded onto study CRFs.

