As of 31 May 2013, one treatment related death has reported in 200 patients treated with crenolanib both as a single agent and in combination. This death occurred during phase Ib evaluation of crenolanib with docetaxel and axitinib in a patient with metastatic NSCLC and liver metastases who developed progressive liver failure and died. This death was classified as possibly related to study drug although progressive metastatic disease in the liver was not excluded.

The most frequent non-hematological grade 1/2 toxicities were diarrhea, nausea, and vomiting (Table 5.2). In patients with GIST, anemia was the most frequent grade 1/2 hematological toxicity associated with crenolanib treatment. Four patients required transfusion, though most of these patients had grade 1/2 anemia prior to treatment initiation. The most commonly reported all-causality events of severity Grades 3 or 4 have included LFT increase, anemia, and decreased lymphocyte count. All LFT abnormalities resolved to baseline or less upon discontinuation of crenolanib. The AML protocol recommends prophylactic antiemetics and anti-diarrheals as well as regular monitoring of hepatic enzymes.

Table 5.2. Incidence of treatment-related AEs occurring in \geq 5% of the study population treated with single agent crenolanib, data as of May 2013

	N	CI CTC Se	verity Gra	de	_	atients =
	GRADE	GRADE	GRADE	GRADE	TOTAL	%
Adverse Event	1	2	3	4	AEs	Patients
Nausea	86	19	2	1	108	63
Vomiting	85	10	4	0	99	55
Diarrhea	62	13	1	0	76	45
Alanine aminotransferase						
increased	32	9	7	2	50	23
GGT increased	33	14	13	3	63	21
Fatigue	16	12	2	0	30	18
Alkaline phosphatase						
increased	25	10	2	0	37	14
Anorexia	15	5	1	0	21	13
Aspartate						
aminotransferase						
increased	28	11	6	2	47	13
Lymphocyte count						
decreased	22	10	7	2	41	13
Headache	14	1	2	0	17	10
Anemia	8	6	4	2	20	10
Abdominal pain	11	2	2	0	15	10
Dyspepsia	7	4	2	0	13	10
Dysgeusia	11	3	0	0	14	9
Constipation	11	2	0	0	13	9
White blood cell						
decreased	16	4	1	0	21	8

Proteinuria	12	0	0	0	12	7
Edema limbs	11	2	0	0	13	6
Hypophosphatemia	10	0	1	0	11	6
Hypoalbuminemia	8	0	0	0	8	6
Periorbital edema	8	0	0	0	8	6
Serum amylase increased	4	3	0	0	7	6
Dizziness	7	0	0	0	7	5
Platelet count decreased	4	0	0	2	6	5

QT prolongation has been observed in only two patients treated with single agent crenolanib

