Appendix V lists the specific standard tests to be performed for this study.

8.11.1 Samples for Standard Laboratory Testing

Blood samples will be collected at the times specified in the Study Schedule (Appendix IV). Standard laboratory tests, including chemistry, liver function tests, and hematology panels, will be performed as outlined below.

- Cycle 1: labs twice weekly (at least 24 hours apart) for the first two weeks of cycle 1, then weekly (±3 days) for the second two weeks of cycle 1
- Cycle 2: labs every 14 days ±4 days
- Cycle 3 to Cycle 6: labs every 28 days ± 14 days
- Cycle 6 onwards: once every two cycles (± 1 cycle)

A pregnancy test should be performed at study entry and at any time during the study if clinically indicated by history or clinical exam. Other clinical laboratory tests will be analyzed by either a central or a local laboratory. Appendix V lists the specific tests that will be performed for this study.

Investigators must document their review of each laboratory safety report

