Appendix IV. Study Schedule

Appendix I	screeni ng					Thera	ару				End of	Follo w-up
Cycle No.				1				2	3	n	Stud	visit
Duration				280			2	8d	28 d	28 d	y visit	
Relative day within cycle	(-)28	1	2	8	1 5	2	1	1 5	1	1		
Baseline Procedure												
Informed Consent	Х											
Inclusion/Exclusion	Х											
Demography, Relevant medical history, current medical conditions including AML- specific history	Х											
Evaluation of FLT3- D835, FLT3-ITD, and other mutational status	Х											
Routine Examination												
Prior/Concomitant medications, significant non- drug therapies	Х	Х					Х		Х	Х	Х	Х
Physical examination ^a	Х	Х					Х			Х	Х	Х
EKG ^b	X	Χ										
Vitals, ECOG Performance Status, Weight	Х	Χ	Х	Х	Х	Х	Х	Х	Х	Х	Х	Х
AEs and SAEs	Х	Χ	Χ	Χ	Χ	Χ	Х	Χ	Х	Х	Х	Х
Laboratory tests												
Hematology ^c	Х	X X		X X	Х	Х	Х	Х	Х	Х	Х	Х
Serum Chemistries ^d	Х	X		X X	Х	Х	Х	Х	Х	Х	Х	Х
HIV, HepB/C	Х											
Urine or serum Pregnancy test	Х										Х	
Peripheral blood for PK analysis ^e		Х	Х		Х		Х		Х			
Peripheral blood for correlative		Х	Х		Χ		Х		Х			

analysis [†]								
Disease assessment								
Bone marrow aspirations (x2) ^g	Х	Χ			Χ	Х	Х	

^a Physical exam can be done within ±4 days of start of cycle 1 and cycle 2 then every 2 cycles

^{c,d} CBC includes platelet count, differential (differential may be omitted if WBC is $<0.5 \times 10^9/L$) and Chemistry panel including creatinie, AST, ALT, and total bilirubin to be drawn twice weekly (at least 24 hours apart) for the first two weeks of cycle 1, once weekly (\pm 3 days) for the second two weeks of cycle 1, bi-weekly (\pm 4 days) for the second cycle and once a month thereof from cycle 3 until cycle 12 (\pm 14 days).

Labs obtained with the local physician can be used for monitoring; PI or designee must review and sign source documents within 24 hours of performance of lab at local physician's office unless performed on a Friday in which case review on the following Monday is acceptable. It is encouraged that labs be performed on Monday thru Thursday.

At the time of any dose escalation, labs should be drawn twice per week for at least one week.

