Appendix V. Clinical Laboratory Tests

Hematology^a Clinical Chemistry^b

Hemoglobin Serum Concentrations of:

Hematocrit Sodium
Erythrocyte count (RBC) Potassium
Leukocytes (WBC) Total bilirubin
Neutrophils, segmented Direct bilirubin
Lymphocytes Indirect bilirubin

Monocytes

Eosinophils Alanine aminotransaminase (ALT/SGPT)
Basophils Aspartate aminotransferase (AST/SGOT)

Platelets

Blood urea nitrogen (BUN)

Creatinine Phosphorus Calcium

Glucose, random

Albumin

Lactate dehydrogenase

Pregnancy Test (serum or urine; females only) a,c,d

Abbreviations: RBC = red blood cells, WBC = white blood cells.

- a Can be performed by local lab
- b Local Lab results may be used for enrollment or dosing decisions
- c Required for women of childbearing potential. Women are considered not of childbearing potential if they are surgically sterile or are postmenopausal. Patients may be entered and enrolled on the basis of a local serum or urine pregnancy test
- d Repeat test as clinically indicated

Protocol: ARO-004

e Repeat test on Day 1 of each cycle of therapy.

Note: Patients may be enrolled on the basis of local chemistries.

Investigators must document their review of each lab report.

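### The chemistry lists, including Appendix V, name neither GGT nor alkaline phosphatase, so elevations of these two enzymes will be under-ascertained, lack a baseline and not be comparable with Table 5.2

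*Combined protocol and SAP*

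**What the plan says.** Four places in the protocol name chemistry analytes.

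- Section 8.1 item 6, at screening: "Creatinine, total bilirubin, ALT, and AST".
- Section 8.2 item 5, on treatment: "Creatinine, total bilirubin, ALT, AST, twice weekly (at least 24 hours apart) for the first two weeks of cycle 1". Draws then become weekly, every two weeks in cycle 2, and monthly from cycle 3 to cycle 12.
- Appendix IV, notes c,d: "Chemistry panel including creatinie, AST, ALT, and total bilirubin to be drawn twice weekly".
- Appendix V, the fullest list: sodium, potassium, total, direct and indirect bilirubin, ALT, AST, BUN, creatinine, phosphorus, calcium, glucose, albumin and LDH.

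Section 8.11.1 also asks for liver function tests without defining them, and then says "Appendix V lists the specific tests that will be performed for this study".

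On known toxicity, Table 5.2 in section 5.5.4 has a row "GGT increased" with 33, 14, 13 and 3 events at grades 1 to 4, in 21% of patients. The alkaline phosphatase row has 25, 10, 2 and 0 events, in 14%. The text above the table says that the AML protocol recommends prophylactic antiemetics and anti-diarrheals "as well as regular monitoring of hepatic enzymes".

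Safety and tolerability is a secondary objective (section 1.2). Section 10.3.9 summarises adverse events by maximum CTCAE grade.

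**The concern.** A laboratory adverse event can be graded only if the analyte is measured, and can be called treatment-emergent only if there is a baseline. If the panel in the plan is followed as written, GGT and alkaline phosphatase will be recorded only where a site happens to run them. Section 11.1.8 justifies frequent blood work as giving every patient the same chance of having a side effect detected. For these two enzymes the plan does not achieve that.

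GGT is not a marginal case, because it has the most grade 3-4 events in the protocol's own toxicity table. Version 4 also changes the dose, from a flat 300 mg/day to BSA-based dosing with a starting dose of up to 400 mg/day (sections 8.6 and 8.7). A GGT or alkaline phosphatase rate below that of Table 5.2 could therefore reflect lack of testing, and the data could not separate that from a real difference.

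**Working it through.** **Inputs.** All 25 rows of Table 5.2 (section 5.5.4); the analyte lists in sections 8.1, 8.2 and 8.11.1 and Appendices IV and V.

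**Step 1: check the table.** Adding grades 1 to 4 in each row reproduces the printed total in all 25 rows. For GGT, 33 + 14 + 13 + 3 = 63, as printed.

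**Step 2: rank rows by grade 3 plus grade 4 events.**

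| Row | Grade 3 | Grade 4 | Sum | All grades | % patients |
|---|---|---|---|---|---|
| GGT increased | 13 | 3 | 16 | 63 | 21 |
| ALT increased | 7 | 2 | 9 | 50 | 23 |
| Lymphocyte count decreased | 7 | 2 | 9 | 41 | 13 |
| AST increased | 6 | 2 | 8 | 47 | 13 |
| Anemia | 4 | 2 | 6 | 20 | 10 |
| Vomiting | 4 | 0 | 4 | 99 | 55 |
| Nausea | 2 | 1 | 3 | 108 | 63 |
| Alkaline phosphatase increased | 2 | 0 | 2 | 37 | 14 |

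No row left out of this table has more than 2. The sum over all 25 rows is 71, so GGT accounts for 16/71 = 23%. The denominator covers only adverse events seen in at least 5% of patients.

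**Step 3: share of liver-enzyme events behind the unlisted analytes.**

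- Grade 3-4: (16 + 2) / (16 + 2 + 9 + 8) = 18/35 = 51%.
- All grades: (63 + 37) / (63 + 37 + 50 + 47) = 100/197 = 51%.

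These are event counts. The table does not say how often GGT rose in a patient whose ALT or AST also rose, so 51% is not a share of affected patients.

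**Step 4: weigh the lists.** Sections 8.1 and 8.2 and Appendix IV give short lists that also leave out sodium, potassium, BUN and other analytes found in Appendix V. Their silence on GGT is therefore weak evidence taken alone. Appendix V is the list that counts, because section 8.11.1 points to it. It names neither enzyme in the text available.

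**Step 5: illustration only.** Suppose the Table 5.2 incidences applied to the 14 planned patients. This is an assumption carried over from other populations, doses and schedules.

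- GGT: 14 x 0.21 = 2.9 patients.
- Alkaline phosphatase: 14 x 0.14 = 2.0 patients.
- At half those incidences: 14 x 0.105 = 1.5 and 14 x 0.07 = 1.0.
- At twice those incidences: 14 x 0.42 = 5.9 and 14 x 0.28 = 3.9.

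The documents do not say how many sites would run these tests anyway, so the share of such patients who would go undetected cannot be calculated.

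**The case against.** A reader might infer that the safety objective would miss known hepatic toxicity. The documents do not support that. ALT, AST and total bilirubin are drawn often, and Appendix V adds direct and indirect bilirubin, albumin and LDH. The two hepatic dose-limiting toxicities and the two dose reductions described in section 8.6 were transaminase events, which this panel measures.

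Nor do the lists break the statement in section 5.5.4 about monitoring hepatic enzymes. Scheduled ALT and AST meet it, and nothing there promises GGT. It would also go too far to say that a low rate will be reported as better tolerability than before, since the safety analysis is descriptive and no comparison with earlier studies is planned.

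The evidence of omission has limits. Appendix V was read from a two-column table in which hematology and chemistry entries run together ("Eosinophils Alanine aminotransaminase (ALT/SGPT", "Basophils Aspartate aminotransferase (AST/SGOT"), and no chemistry entry stands beside monocytes or platelets, so a lost entry cannot be ruled out. The abbreviation list in section 4 defines gamma glutamyl transpeptidase, which may mean that the test was intended. Appendix IV describes its panel as including the named tests, so it is not exhaustive, and section 8.11.1 mentions liver function tests apart from chemistry. These points lower confidence but do not close the gap: a non-exhaustive or undefined term does not require a test, section 8.11.1 refers back to Appendix V, and no procedure calls for GGT.

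The case for alkaline phosphatase is the weaker of the two. It rests on the 14% all-grade frequency, not on its two grade 3 events.

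**Conclusion.** The point holds in a limited form. As the text stands, no list requires GGT or alkaline phosphatase at baseline or on treatment. Their elevations will be under-ascertained, cannot be shown to be treatment-emergent, and will not be comparable with Table 5.2. Transaminase and bilirubin toxicity is still captured.

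The gap concerns the row with the most grade 3-4 events in Table 5.2 (16 of 71 tabulated events). Together the two enzymes account for 18 of 35 grade 3-4 liver-enzyme events. Both figures count events, within a table cut off at 5% incidence.

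The conclusion assumes that Appendix V lost no entry when it was read from PDF. If the original table does list GGT and alkaline phosphatase, what remains is that sections 8.1 and 8.2 and Appendix IV should be brought into line with it. The primary endpoint is not affected.

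**What to change.** First check Appendix V in the source document. If the two enzymes are absent, add GGT, and alkaline phosphatase on the strength of its all-grade frequency, to Appendix V, section 8.1 item 6, section 8.2 item 5 and Appendix IV notes c,d, at baseline and at every scheduled chemistry draw. Define liver function tests in section 8.11.1 by reference to that list. In section 10.3.9, tabulate both by maximum CTCAE grade with shift from baseline. If the sponsor prefers to leave them out, the protocol should justify this against Table 5.2 and the study report should say that they were not systematically measured.

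The cost is two analytes on blood already drawn, plus the amendment wording. There are two downsides. The safety table will look less favourable. Grade 3-4 GGT findings could also interact with the dose-modification rules in Tables 8.3 and 8.5 and with the accrual stop at more than 33% unacceptable toxicity (section 10.3.7 and the Synopsis). The sponsor must state how those passages apply to GGT and alkaline phosphatase; no clinical rule is proposed here.
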